4.1 Subpopulations

The Safety-2nd Dose and ITT-2nd Dose populations will be further classified as rescue or recurrence populations. Subjects who took a second dose will be classified as either rescue or recurrence as follows:

- **Rescue:** subjects who did not achieve headache pain-free at 2 hours, completed the 2-hour assessments, and took a second dose of study drug between 2 hours and 24 hours post first dose.
- **Recurrence:** subjects who achieved headache pain-free at 2 hours, but then experienced recurrence of mild, moderate, or severe migraine pain and took a second dose of study drug up to 24 hours from the first dose.

4.2 Exclusions from Per-protocol population

The following protocol deviations are considered major and might impact the assessment of efficacy. These deviations would exclude subjects from the PP population.

- Any violation of the following inclusion/exclusion criteria:
Inclusion criteria:
 2. Subjects with migraine with or without aura fulfilling the International Headache Society (IHS) diagnostic criteria 1.1 and 1.2.1 (International Headache Classification (ICHD)-2004).
 4. MIDAS score ≥ 11 .
 6. History of 3-8 migraine attacks per month (< 15 headache days per month).

Exclusion criteria:

12. Previous participation in this clinical trial.
15. History, within past 12 months, of chronic migraine or other forms of primary or secondary chronic headache disorder (e.g. hemicranias continua, medication overuse headache) where headache frequency is greater than or equal to 15 headache days per month.
16. Use of more than 3 doses per month of either opiates or barbiturates.

The criteria violations above will be identified from entries on CRF page Inclusion/Exclusion Criteria or explicitly recorded in Protocol Deviations log.

- First Treatment with study drug beyond 4 hours after the onset of migraine
- Use of triptans and ergots as concomitant medications within 24 hours of study drug administration. As concomitant medications are entered in the CRF with start dates but not times, this 24-hour period will be identified as the date of dosing and the next day. Use of excluded rescue (concomitant) medications before 24 hours after dosing or use of any early

rescue medication (study drug or not) before 2-hour time point. Cases of early rescue medication use will be identified from e-diary entries. Cases of using excluded rescue medication will be identified from concomitant medications data with an entered indication entry that indicates use for migraine. (A listing of all rescue medications will be generated and reviewed prior to study unblinding, and will be used to evaluate this protocol deviation.) As concomitant medications are entered in the CRF with start dates but not times, the 24-hour period will be identified as the date of dosing and the next day.

- Subject begins, or has a change in ongoing medication to reduce the frequency of migraine episodes after randomization. These medications will be identified by drug indication that includes the string “MIGR,” and the string “PROPH” or “MIGR,” and the string “PREV,” and a dosing frequency that does not indicate as-needed use from the concomitant medication page of the CRF. If such a drug is on the migraine history page without a stop date, even if not on concomitant medications page, the subject will be interpreted to be stable on it and the drug will not be considered to represent a deviation for this category. (A listing of all rescue medications will be generated and reviewed prior to study unblinding, and will be used to evaluate this protocol deviation.)
- Subject did not receive study drug as assigned
- Subject did not treat a migraine of at least mild severity
- Subject takes only one of the two required tablets for first dose. These will be identified from entries on the Dosing form of CRF. Entries include counts of tablets dispensed and returned, and comments associated with dispensing and return.

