#### **7.3.1 Rescue Medication**

Rescue medication will be permitted after completion of the 2 hour assessments if the migraine does not respond (subject is not headache pain free). If the migraine does not respond within 2 hours a second dose of randomized study drug may be taken up to 24 hours after the first dose as long as no other rescue medication has been used. The Investigator may advise each subject as to an alternative suitable rescue medication. Triptans, ergots, opioids and barbiturates **MUST NOT** be used for rescue medication within 24 hours of study drug administration. The use of rescue medication will be recorded in the subject diary.

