## 10.3 Analysis Populations

### 10.3.1 Primary efficacy – FIRST dose

The statistical analysis of the first dose will be based on the analysis populations as defined below:

Safety population	All randomized subjects who use at least one dose of study drug, regardless of whether or not they undergo any study assessments. Subjects are evaluated by the drug they use, not by the drug to which they are randomized.
ITT population	All randomized subjects who use at least one dose of study drug and have any post-dose assessments. Subjects are evaluated by the drug to which they are randomized.
mITT population	All randomized subjects who use at least one dose of study drug to treat a qualifying migraine attack and have any post-dose assessments. Subjects are evaluated by the drug to which they are randomized.

**PP population** All ITT subjects will be considered per protocol (PP) if they dose a migraine attack and do not deviate from the protocol.

The following is a list of additional protocol violations which would exclude subjects from the PP population:

- Subject received excluded rescue medications or used rescue medication before 2 hour time point.
- Subject used recurrence medication before 2 hour time point.
- Subject did not receive study drug as assigned.
- Subject did not meet all inclusion/exclusion criteria.
- Subject did not treat a migraine of at least moderate severity.

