	2	Power	99.90%	>99.99%	>99.99%	>99.99%	>99.99%
		Sample Size	450	450	450	450	450
	3	Power	>99.99%	>99.99%	>99.99%	>99.99%	>99.99%
		Sample Size	575	575	575	575	575
	4	Power	99.90%	>99.99%	>99.99%	>99.99%	>99.99%
		Sample Size	450	450	450	450	450
Placebo vs D200	1	Power	70.87%	70.87%	72.97%	71.17%	68.47%
		Sample Size	570	570	570	570	570
	2	Power	84.40%	85.00%	85.80%	85.90%	85.80%
		Sample Size	450	450	450	450	450
	3	Power	83.50%	83.20%	81.30%	83.40%	81.80%
		Sample Size	575	575	575	575	575
	4	Power	90.20%	90.50%	92.50%	91.40%	90.40%
		Sample Size	450	450	450	450	450

It is expected for a one-sided, two-sample comparison of proportions at the 2.5% level of significance, a sample size of 570 subjects per treatment group (as defined by the first dose) provides >90% power to detect a difference in headache pain-free response rates for assumed true rates of 7.4% and 18.8% (placebo and 200 mg), 7.4% and 13.6% (placebo and 100 mg), and 7.4% and 13.9% (placebo and 50 mg) >90 % power for MBS for both the 50 mg dose arm and the 100 mg dose arm and very near or higher than 80% power for MBS in the 200 mg dose arm.

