11 EFFICACY ANALYSES

This section details the specifications for summarizing efficacy endpoints.

The primary and key secondary efficacy analyses will be performed on the ITT, mITT, and PP populations. The primary analysis population is the mITT population. Exploratory efficacy analyses will be performed on the ITT and ITT-2nd Dose populations, depending on the endpoint. Efficacy responses will also be presented in a listing.

Unless otherwise stated, all primary, secondary, and exploratory efficacy hypotheses will be tested using a logistic regression model with treatment group and background use of medication to reduce the frequency of migraine episodes as covariates. For treatment comparisons, an estimate of the odds ratio of achieving a response, as well as the corresponding confidence interval and p-value using Wald's test, will be computed. Tests of the primary and key secondary endpoints will be conducted at a one-sided significance level of 0.025; tests of all other endpoints will be conducted at a two-sided significance level of 0.05.

Analyses of second-dose endpoints with too few subjects in the treatment-sequence-subpopulation groups may have too little data separation for a logistic regression model to reach a stable solution. For these models, the "Firth" modification of the maximum likelihood estimation will be used to achieve a solution.

The efficacy endpoints will depend on data collected by e-diary that depends on subject's response entry in the correct order and at the expected scheduled e-diary assessment times. Assessment times are analyzed as calculated by the e-diary and not as part of analysis programming.

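### The SAP's per-protocol rules remove subjects for medication events after the 2-hour assessment, so the supportive PP analysis of the 2-hour endpoints is conditioned on a post-outcome event

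*SAP*

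**What the plan says.** SAP 4.2 lists the major deviations that remove a subject from the PP set. Three concern medication.

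- Triptans or ergots within 24 hours of study drug. CRF medication entries have a start date but no time, so "this 24-hour period will be identified as the date of dosing and the next day".
- Barred rescue drugs, in these words: "Use of excluded rescue (concomitant) medications before 24 hours after dosing". The same two calendar dates put this into practice. The same bullet excludes for any rescue before 2 hours, which is identified from the e-diary.
- In a separate bullet with no end date: "Subject begins, or has a change in ongoing medication to reduce the frequency of migraine episodes after randomization".

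Protocol 7.3.1 ties rescue to the outcome: "Rescue medication will be permitted after completion of the 2 hour assessments if the migraine does not respond", where response means pain free. It bars triptans, ergots, opioids and barbiturates as rescue within 24 hours of study drug. Protocol 10.3.1 already has a PP exclusion of this kind: "Subject received excluded rescue medications or used rescue medication before 2 hour time point".

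Under SAP 11 the primary and key secondary analyses are run on the ITT, mITT and PP sets, with mITT primary. "Tests of the primary and key secondary endpoints will be conducted at a one-sided significance level of 0.025". The effect measure is an odds ratio from logistic regression with a Wald test. Protocol 10.5 calls the PP analyses supportive.

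**The concern.** All six confirmatory comparisons use the 2-hour diary entry. A drug taken after that entry cannot change it. SAP 11.2 applies the same logic in the primary analysis, where only rescue within the first two hours turns a subject into a non-responder.

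The PP rule goes further and deletes the subject for later use. Since rescue is offered to subjects who are not pain free at 2 hours, those deleted for late excluded rescue will mostly be 2-hour failures. The PP estimate is then conditioned on something that follows from the outcome. If failures in one arm turn to excluded drugs more often than in another, the PP odds ratio moves with no change in drug effect.

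The design offers one reason why use might differ. In SAP 2.3 the placebo arm's second dose is always placebo, while two of the three second-dose entries listed for each lasmiditan arm are active. That is an inference; the documents give no rates.

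A late preventive change is also a post-outcome event, but the documents do not link it to 2-hour failure as they do rescue.

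At stake is how far agreement or disagreement between PP and mITT can be read as a check on adherence.

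**Working it through.** **Inputs from the documents.** Planning pain-free rates (SAP 2.2): placebo 7.4%, 200 mg 18.8%, 100 mg 13.6%, 50 mg 13.9%. Evaluable subjects: 570 per arm. One-sided alpha 0.025.

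**Assumption.** Let f be the share of an arm's 2-hour failures removed from PP for late excluded medication. The documents do not give f; 2% to 20% is used as a range. For simplicity, no 2-hour responders are removed and the covariate is ignored.

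**Plan's own figure.** With n = 570, p̄ the mean of the two rates p0 and p1, and z = 1.96:

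power = Φ{[(p1 − p0) − z√(2p̄(1 − p̄)/n)] / √[(p0(1 − p0) + p1(1 − p1))/n]}

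For 100 mg: (0.062 − 0.0356)/0.0181 = 1.46, so power is 92.8%. The same formula gives 94.6% for 50 mg and 99.99% for 200 mg. The SAP's claim of more than 90% for each dose is reproduced.

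**Effect of removal.** PP rate = p / [p + (1 − p)(1 − f)]. The odds of response in an arm are therefore divided by (1 − f), and

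OR in PP = OR × (1 − f placebo)/(1 − f lasmiditan).

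For 200 mg, OR = (0.188/0.812)/(0.074/0.926) = 2.897. With 10% removed on placebo and 5% on 200 mg: 2.897 × 0.90/0.95 = 2.745. Reversed: 2.897 × 0.95/0.90 = 3.058.

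| f placebo | f 200 mg | Placebo % | 200 mg % | Difference (points) | OR | One-sided error under the null |
|---|---|---|---|---|---|---|
| 0 | 0 | 7.4 | 18.8 | 11.4 | 2.897 | 0.025 |
| 5% | 5% | 7.8 | 19.6 | 11.8 | 2.897 | 0.025 |
| 10% | 10% | 8.2 | 20.5 | 12.3 | 2.897 | 0.025 |
| 5% | 2% | 7.8 | 19.1 | 11.4 | 2.809 | 0.018 |
| 2% | 5% | 7.5 | 19.6 | 12.1 | 2.989 | 0.034 |
| 10% | 5% | 8.2 | 19.6 | 11.4 | 2.745 | 0.014 |
| 5% | 10% | 7.8 | 20.5 | 12.7 | 3.058 | 0.043 |
| 20% | 10% | 9.1 | 20.5 | 11.4 | 2.575 | 0.007 |
| 10% | 20% | 8.2 | 22.4 | 14.3 | 3.259 | 0.0745 |

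The last column sets both true rates to 7.4%. For 10%/5%, 570 × (0.074 + 0.926 × 0.90) = 517 placebo subjects and 570 × (0.074 + 0.926 × 0.95) = 544 active subjects remain. Then ln(0.90/0.95) = −0.054, the standard error is 0.227, and Φ(−0.054/0.227 − 1.96) = 0.014. Reversing the sign of the first term gives 0.043.

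For 100 mg the OR is 1.970. Under 10%/5% it falls to 1.866, and Wald power goes from 92.0% to 87.0%. Under 5%/10% it rises to 2.079, with power 95.2%.

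**Window.** For a dose at clock hour h, the dosing date plus the next day covers 48 − h hours after the dose and h hours before it. Forward cover is therefore 24 to 48 hours. An 08:00 dose has 40 hours covered after it and 8 before, so 16 of the preceding 24 hours fall on the uncounted previous date. A 22:00 dose leaves 2 hours uncounted.

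**The case against.** **The scale matters.** A reader might infer that the PP analysis inflates the drug effect, because the 200 mg difference grows from 11.4 to 12.3 points at 10% removal in both arms. The documents do not support that: the planned measure is the odds ratio, and equal removal leaves it and its null error rate unchanged. Bias needs unequal removal, for which there are no figures, and the direction could be against lasmiditan. This stands.

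**Selected on the primary endpoint is too strong.** Failures who use permitted rescue, including the second study dose, stay in. Pain-free subjects who recur and take an excluded drug leave. Selection is on a drug event linked to failure, not on failure itself.

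**PP serves later times too.** SAP 11.7.1 and 11.7.3 report PP results at 3, 4, 24 and 48 hours, where later rescue can matter. This stands and limits the change to the 2-hour analyses.

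**The rules follow the protocol.** Protocol 10.3.1 names excluded rescue with no evident 2-hour limit on that part. Protocol 7.4 requires withdrawal for a preventive change, and the SAP bullet also catches changes before dosing. Both are true, but neither makes a later event relevant to a 2-hour reading.

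**Safeguards.** Membership is fixed before unblinding (SAP 4), and exclusions are tabulated by reason and treatment sequence (SAP 7). Blinding does not undo conditioning on a post-outcome event. The table would show unequal exclusion counts by sequence but is not planned by 2-hour response.

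**Day-before triptans.** A reader might take the uncounted previous date as further outcome selection. It is not. Protocol 7.3.1 and 9.1.7 bar these drugs as rescue, 9.1.7 states no washout from an earlier attack, and medication taken earlier for the same attack already counts as non-response (SAP 11.2). What remains is an ambiguity in the SAP about whether its 24 hours run backwards.

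**Conclusion.** The point holds for the supportive PP analysis of the primary and key secondary endpoints. Exclusions for rescue, triptan or ergot use after the 2-hour assessment, and for later preventive changes, cannot be justified by any effect on a 2-hour outcome. For rescue, Protocol 7.3.1 makes the link to failure explicit.

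The size is unknown. Assumed shares of 10% and 5% move the 200 mg odds ratio by about 5% either way. The null error figures describe the PP test taken alone; they are not the trial's type I error, because no confirmatory claim rests on PP. The mITT result is unaffected. This is an inexpensive improvement to a secondary check, not a threat to the trial's conclusion.

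**What to change.** 1. For PP analyses of the 2-hour endpoints, exclude only for medication deviations up to the 2-hour assessment and for preventive changes between randomization and the first dose. Use the e-diary answer for timing, since SAP 8.5 already separates other migraine medication before and after that assessment. Settle date-only records on the dosing day by blinded review.
2. List later excluded medication and later preventive changes as deviations that do not remove the subject from these analyses.
3. Keep the existing rule for PP summaries after 2 hours.
4. Record the departure from Protocol 10.3.1 in SAP 5.1.
5. Reconcile the 24-hour wording in SAP 4.2 with Protocol 7.3.1 and 9.1.7, and state whether the window looks back before dosing. If it does, the date rule must include the previous calendar day.

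Cost: SAP text, a second PP flag specific to 2 hours, and blinded review of some date-only records, all before unblinding. No new data are needed.

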## 7.4 Prohibited Medications

Use of the following medications is prohibited for the duration of a subject's participation in the study from **Screening/Visit 1** through **EoS/Visit 2**:

- Any investigational treatment other than lasmiditan.
- All other symptom modifying treatments (e.g. antiemetics) for migraine except rescue or recurrence medication as detailed in [Section 7.3.1](#) and [7.3.2](#).
- If a patient requires the initiation of migraine prophylaxis (concomitant medication to reduce the frequency of migraine episodes) or a change in ongoing migraine prophylaxis after the **Screening/Visit 1** they should be withdrawn from the study.

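### The SAP's per-protocol rule does not flag a post-randomization change in a migraine preventive that the migraine history page lists as ongoing

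*SAP*

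**What the plan says.** The relevant bullet in SAP 4.2 has four parts.

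- **The deviation.** "Subject begins, or has a change in ongoing medication to reduce the frequency of migraine episodes after randomization". It has two limbs: starting a preventive, and changing one already in use.
- **How candidate drugs are found.** By text strings in the indication (migraine together with prophylaxis or prevention) and "a dosing frequency that does not indicate as-needed use from the concomitant medication page of the CRF".
- **The exemption.** "If such a drug is on the migraine history page without a stop date, even if not on concomitant medications page", then "the subject will be interpreted to be stable on it and the drug will not be considered to represent a deviation for this category".
- **The review.** "A listing of all rescue medications will be generated and reviewed prior to study unblinding, and will be used to evaluate this protocol deviation".

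Protocol 7.4 deals with both limbs together. It covers the case "If a patient requires the initiation of migraine prophylaxis" and equally "a change in ongoing migraine prophylaxis after the" screening visit, and says such a patient should be withdrawn. Protocol 10.3.1 requires PP subjects not to deviate from the protocol. SAP 4 narrows this to mITT subjects without any of the major deviations listed in 4.2, and this bullet is on that list.

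**The concern.** The exemption answers a different question from the one the second limb asks. A history-page entry with no stop date shows that the subject was taking the drug at entry. It does not show that the regimen stayed the same afterwards. Yet the SAP infers stability from it and then rules the drug out as a deviation.

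A subject already on a preventive at screening is the person to whom the second limb is addressed, and is also the person most likely to have the drug on the history page as ongoing. For that record the exemption overrides the limb.

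At stake is whether the PP set is what the SAP says it is. PP is meant to show whether the result holds among subjects free of deviations that could affect the efficacy assessment. As written, it can retain subjects with a deviation that the SAP itself calls major.

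**Working it through.** The plan gives no figure on this point, so there is nothing to reproduce and no arithmetic applies. The check is to apply the rule, as written, to each way a preventive can be started or changed.

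**Reading the exemption.** Its condition is the history-page entry without a stop date. The words about absence from the concomitant page begin with *even if*, so the exemption holds whether or not the drug is also on that page. It therefore still applies when the concomitant page shows a new dose or frequency.

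**What the history page can show.** Protocol 9.1.1 has migraine history, including prior treatment, recorded as part of the medical history. The Schedule of Assessments places that review at Visit 1 only, the visit at which the subject is randomized. Unless the page is updated later, it describes the position at randomization and cannot show what happened after it.

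**Cases.**

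1. New preventive started after randomization, not on the history page: flagged as a start.
2. Preventive on the history page without a stop date, dose or frequency changed after randomization, change recorded on the concomitant page: **not flagged**.
3. As case 2, but the change is not on the concomitant page: **not flagged**.
4. Ongoing preventive recorded only on the concomitant page, then changed: the exemption does not apply, so it can be flagged.
5. Preventive stopped after randomization, with a stop date entered on the history page: the exemption does not apply, so it can be flagged if the drug is on the concomitant page.
6. Switch to a different preventive: the new drug can be flagged as a start.

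The rule fails in cases 2 and 3. If a drug is stopped and the stop is recorded somewhere other than the history page, the exemption's condition is still met and the result is the same.

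**Whether anything else in the plan removes these subjects from PP.**

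- The review listing is of rescue medications, in the same words as the preceding bullet on rescue use. A preventive taken on a schedule is not rescue medication.
- SAP 4.2 names the Protocol Deviations log as a source for violations of the listed inclusion and exclusion criteria. It does not name it for this bullet.
- Exclusion criterion 17, on preventive changes in the three months before screening, is not among the criteria that remove a subject from PP (inclusion 2, 4 and 6; exclusion 12, 15 and 16). This bullet is the only PP rule on preventive stability.
- SAP 7 lists all deviations, but listing does not remove anyone from PP.
- Withdrawal under Protocol 7.4 before an attack is treated keeps the subject out of ITT, and so out of PP. Withdrawal is not itself a PP exclusion in 4.2, so a subject who was not withdrawn and then treated an attack stays in.
- SAP 5.1, which records changes from the planned analysis, does not mention this narrowing.

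**The case against.** The exemption has a sensible use. A long-standing preventive entered on the concomitant page could look like a new start, and the history page shows that it is not. That stands, but it justifies the exemption only for the starting limb.

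The CRF is not in the documents. If sites record a dose change by closing the history-page row with a stop date and opening a new one, the exemption's condition fails and the change can be caught. This is a fair limit on how often the gap would matter. It does not mend the rule, because the SAP states no such convention. Protocol 7.3 says only that changes in dosage or new medications arising from intercurrent illness go into the CRFs, without naming a page.

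The word *rescue* in the review sentence looks carried over from the bullet above, and the stated purpose is to evaluate this deviation. The reviewers may therefore intend to look at preventives. That is plausible, but the listing as described would not show them, and the text gives no power to override the exemption.

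A reader might infer that the second limb can never operate. Cases 4 and 5 show that it can, and case 6 is caught by the first limb.

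A reader might also infer that the stratum covariate becomes wrong for these subjects. The documents do not support that. The stratum in SAP 2.3 is yes or no for current use at randomization, and a subject whose dose is altered is still a user. Errors in assigning the stratum have their own sensitivity analysis in SAP 11.4.

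**Conclusion.** The point holds in a limited form. A post-randomization change in a preventive listed as ongoing on the migraine history page is not flagged by this rule, even when the concomitant page shows the change. The bullet contradicts the deviation it names, and the result is at odds with Protocol 7.4 and with the PP definition in Protocol 10.3.1.

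Its size cannot be computed. An affected subject must have a preventive on the history page without a stop date, have it changed after randomization, not be withdrawn under Protocol 7.4, and then treat an attack that qualifies for mITT. The documents give no rate for any of these steps, so a count per arm would rest entirely on outside assumptions.

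The consequence is minor. SAP 11 makes mITT the primary population, so the primary test and the gatekept sequence are untouched. What is affected is the supportive PP analysis of the primary and key secondary endpoints, together with the PP summaries at other time points (SAP 11.7.1 and 11.7.3) and the SAP 7 table of reasons for exclusion from PP. The direction of any effect on a PP estimate cannot be inferred from the documents. The conclusion assumes that the history page is not routinely updated after Visit 1 and that the exemption is programmed as written.

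**What to change.** Amend the bullet in SAP 4.2 in two places.

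1. Apply the exemption only when the CRF shows no dose, frequency or stop change for that drug between randomization and first dose. Otherwise flag the subject. State that window expressly, because the bullet now gives a start (randomization) but no end.
2. Base the pre-unblinding review for this bullet on a listing of preventive medications, taken from both the migraine history and concomitant medication pages, instead of a listing of rescue medications.

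The sponsor should also confirm how sites record a regimen change for a drug already on the history page, so that the programmed check looks in the right place.

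The cost is a wording change and one extra listing, and a few subjects may leave PP. SAP 4 finalizes the populations before unblinding, so the change can be made blind to treatment. The withdrawal provision in Protocol 7.4 is not in question here; the two documents need only be reconciled on how such subjects are classified for PP.
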